## 6.1.2.2 *Mechanistic:*

The primary mechanistic evaluation will be extended to selected sperm collected from the 45:90 (or 40:80) interface of DGC washed samples. We wish specifically to determine the relationship between chromatin compaction and nuclear integrity in these interface samples with the HBS of their corresponding pellets.

### 7. TRIAL DESIGN

A parallel group, two arm, multicentre blinded, efficacy clinical trial with mechanistic evaluation.

## 7.1 Setting

Assisted Conception or Reproductive Medicine Units where IVF-ICSI is practiced and other relevant clinical settings.

## 7.2 Allocation

Randomisation into PVP-ICSI (non-intervention) or PICSI (intervention) groups

### 7.3 Main Endpoint

LBR at  $\geq$ 37 weeks' gestation following a ICSI treatment with first fresh embryo transfer cycle in randomised couples.

### 7.4 Intervention Model

Parallel Assignment

### 7.5 Masking

Blinded –participants, clinical care providers in IVF-licensed unit, maternity and neonatal wards, research nurse responsible for participants follow-up will be blinded. The only unblinded group at study sites is going to be embryologists who perform ICSI/PICSI and HBS procedures and who will be also responsible for couple randomisation; in PCTU they will be study Data Manger and independent statistician who will prepare reports for the DMEC. HBS in relation to arm allocation will be known to scorer only.

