#### **10.4 Participant Intervention**

Couples will follow the guidance and procedures required for IVF preparation according to the centre involved (which as NHS units follow standard ICSI procedures – with the quality control assessment provided by UKNEQAS). For standard ICSI, it is normal practice for eggs to be

injected with sperm a few hours after egg collection. The embryologist or andrologist will prepare the semen samples by density gradient (DG) washing. Couples will then be randomised into one of the two arms and the prepared sperm will be processed through either modified (PICSI) or standard (PVP-ICSI) procedures by the embryologist. The operating procedures for PICSI and PVP-ICSI will be standardised across centres and integrated into their SOP Quality Management Systems as required by Human Fertilisation and Embryology Authority (HFEA). Prepared (pelleted) sperm samples will be used to obtain hyaluronan binding score (HBS). Injected eggs will be incubated overnight to allow pronucleate zygotes (PNZ) to form by Day 1. Once all ICSI procedures, including HBA scoring have been completed on Day 0, any remaining sperm sample will be processed according to Section 11.8.1 for the mechanistic research evaluation.

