### 11.9 Selection of Samples for Laboratory Mechanistic Assessments

The Birmingham Mechanistic Laboratory will thaw out single aliquots and cytology will be performed on all or as many of the 3730 trial samples as possible. Cytology provides an important primary benchmark on the integrity of the semen samples

The mechanistic evaluations will be performed following PCTU stratification of the clinical HBS values (three scoring strata: <50%, 50-65%, >65%, HBS). The routine cytology will then determine if there is sufficient sample available; it is anticipated that a significant proportion of the samples will have insufficient sperm for further mechanistic evaluation. However, the stratification will generate a balanced sampling framework from each trial arm across the three HBS strata. Those samples identified by PCTU from their HBS for the mechanistic evaluation will be communicated to the HBRC central sample repository. The HBRC will then coordinate sample transfer to the four mechanistic laboratories to perform the hierarchy of mechanistic test evaluations as described in Figure 5 and Table 3.

In summary, the PCTU will select the HABSelect semen samples to be used for mechanistic analysis based on HBS and communicate this to the HBRC who will arrange shipment to the appropriate Mechanistic Laboratories. This process can be reiterated until ~900\* samples have been tested with each assay across the three, <50% 50-65%, >65%, HBS strata. It is anticipated that access to screening the full complement of 3730 trial samples in order to achieve this may be required. With dynamic PCTU and Birmingham monitoring of sample selection for analysis, it will be possible to obtain high quality information for each test in each stratum even if only a minority of samples is amenable to global examination by *all* tests. Local statistical support is confident that the information can be integrated. Shipment of samples to the mechanistic labs will follow the same operating procedures as transport of the samples from the participating centres to the central storage bank.

\* Belfast will take 450 samples for analysis but will analyse them using two distinct variations of the comet assay.

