## 13.6 Statistical Analysis

## 13.6.1 Clinical Evaluation

Our unit of analysis will be couples randomised to alternative interventions. In addressing the research question in this grant application, we have elected to focus on the outcome of the ICSI cycle with first fresh embryo transfer in each randomised couple and powered the trial accordingly. We believe that, if effective, the impact of the intervention will be evident in the first fresh study cycle. Attempting to evaluate cumulative live birth rates after an ICSI treatment culminating in transfer of fresh embryos followed by the subsequent transfer of frozen embryos in those not achieving a pregnancy would require an extended duration of follow-up. This would significantly increase the complexity and costs of the proposed trial, without generating outcomes of sufficient additional value.

Numbers of couples who are eligible, recruited, and followed up will be recorded in a CONSORT flow-chart. Baseline characteristics of couples in each arm will be tabulated. Outcomes in intervention and non-intervention arms will be compared using multivariable regression with effects summarised as odds ratios with 95% confidence intervals.

If there is evidence that the clinical pregnancy rate differs between the trial arms, then secondary analyses will be carried out taking only women with a clinical pregnancy as the denominator.

Sensitivity analyses will be carried out which adjust for other potentially prognostic factors in addition to the minimisation factors. Factors to be included will be selected blind to their distribution between recruitment arms or the effect of treatment on outcome, and will be those that are associated with the outcome or believed a priori to be prognostic.

In all cases, results of primary analyses will be given more weight than those of the secondary analyses.

**Subgroup analyses.** For binary outcomes, results will be expressed as odds ratio with 95% confidence intervals of pregnancy success in either arm. The exploratory subgroup analyses

- Hyaluronan Binding Score; HBS (High (>65%) versus low (≤65%)),
- maternal age (≤35 years versus >35),
- Previous miscarriages (none versus any),
- FSH hormone level (<6.0miU/ml versus ≥6.0miU/ml ) or AMH hormone level (<17pmol/L versus ≥17pmol/L) where FSH testing is not available.
- sperm concentration (<15mml versus ≥15mml).
- We may also analyse a very low (≤25%) vs. low (>25%, ≤65%) HBS sub-group.

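### The HBS reader knows the arm and nothing requires HBS to be read before allocation, yet the mechanistic strata, the structural model and an exploratory subgroup treat HBS as independent of arm

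*Protocol*

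**What the plan says.** On masking, section 7.5 says "The only unblinded group at study sites is going to be embryologists who perform ICSI/PICSI and HBS procedures", and gives the same embryologists the task of randomising couples. It adds that "HBS in relation to arm allocation will be known to scorer only".

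On the order of work, section 10.4 has the semen prepared by density gradient and continues: "Couples will then be randomised into one of the two arms and the prepared sperm will be processed" by PICSI or PVP-ICSI. HBS on the prepared pellet is mentioned after that. The only stated time limit is completion on the day: "Once all ICSI procedures, including HBA scoring have been completed on Day 0". Section 9.6 keeps HBS out of the minimisation for logistical reasons.

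On use, section 6.1.1.2 makes HBS in relation to chromatin integrity and live birth a primary mechanistic objective. Sections 11.9 and 13.5 sample by clinic HBS in three bands (<50%, 50–65%, >65%) and rely on the result that "the stratification will generate a balanced sampling framework from each trial arm across the three HBS strata". Section 13.7 puts HBS between the laboratory assays and the clinical outcomes in the structural equation model. Section 13.6.1 lists HBS, cut at 65%, first among the exploratory subgroups.

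On checks, section 11.8.3 reviews HBS every four months to find deviating centres. Section 11.8.1 has some samples re-scored after thawing, and section 13.1.2.2 makes the correlation of clinical with post-clinical scores a secondary mechanistic outcome.

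**The concern.** The pellet's true binding cannot depend on the arm, because the sample is prepared before the couple is randomised. The reading can. It is made at the microscope by someone who, by section 7.5, knows the allocation, and in the order that section 10.4 describes, the allocation already exists when the reading is made. Under section 10.2 only the PICSI arm has its sperm placed on a hyaluronan surface before pick-up, so only that arm could give the reader any prior impression of the property that HBS measures.

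If readings differed by arm, men above and below a cut-point would not be the same kind of men in the two arms, and a comparison of arms within an HBS band would no longer be protected by randomisation. Sampling equal numbers from each arm within HBS bands would not repair this, because the bands are built from the same score. What is at stake is the mechanistic evaluation and the HBS-by-treatment comparison.

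**Working it through.** **Reading the sections together.** Unmasked reader: stated in 7.5. Allocation before HBS: the narrative order in 10.4, not an express rule. Requirement to read HBS before allocation, or by a masked reader: none found. Comparison of HBS between arms: none stated in 11.8.1, 11.8.3 or 13.1.2.2. The protocol has no figure of its own to reproduce on this point, so what follows is illustration only.

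**Inputs.** About 10% of samples below 50% (section 13.5). Share at or below 65%: 121/(121 + 357) = 121/478 = 25.3% (Table 2, section 5.3.2). Overall live birth 24% (sections 5.1 and 5.4.4). Assumptions with no source in the protocol: the size of the reading shift, and a low-to-high HBS ratio of live birth equal to the PVP clinical pregnancy ratio in Table 2, 37.9/51.1 = 0.74.

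**Membership, normal model.** From z(0.10) = −1.282 and z(0.253) = −0.665: SD = (65 − 50)/(1.282 − 0.665) ≈ 24.3 and mean = 50 + 1.282 × 24.3 ≈ 81.2. If one arm is read 5 points high, P(≤65) = Φ((65 − 86.2)/24.3) = 0.192. If it is read 5 points low, P(≤65) = Φ((65 − 76.2)/24.3) = 0.323. The <50% band moves from 10% to 6.8% or 14.1%.

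**Membership, beta model.** The normal model puts about 22% of men above 100%, so I refitted a beta distribution to the same two points (parameters 3.71 and 1.19).

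**Effect on the odds ratios.** On the beta model I took logit(live birth) = −2.04 + 1.158 × HBS (as a fraction). This gives 24% overall, 19.0% at or below 65% and 25.7% above. There is no true treatment effect; only the PICSI-arm reading is shifted.

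| PICSI-arm shift | Share ≤65%, PICSI (PVP 25.3%) | OR, low HBS | OR, high HBS | Interaction ratio |
|---|---|---|---|---|
| −10 | 41.5% | 1.09 | 1.04 | 1.05 |
| −5 | 32.7% | 1.05 | 1.02 | 1.02 |
| −3 | 29.6% | 1.03 | 1.01 | 1.02 |
| 0 | 25.3% | 1.00 | 1.00 | 1.00 |
| +3 | 21.5% | 0.97 | 0.99 | 0.98 |
| +5 | 19.1% | 0.96 | 0.98 | 0.97 |
| +10 | 14.0% | 0.91 | 0.97 | 0.95 |

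**Scale against sampling error.** With the 3,357 outcomes of section 13.4.1, the low-HBS group holds about 0.253 × 3,357 ≈ 849 couples, or 425 per arm. SE of the log odds ratio ≈ √(2/(425 × 0.190 × 0.810)) = 0.175. A 5-point shift upwards gives ln 0.956 = −0.045, about a quarter of one standard error.

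**The case against.** Several points on the other side are sound.

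- No sentence fixes HBS after injection. The schedule in section 11 even lists HBS above ICSI/PICSI, although both fall on Day 0 and row order is not a rule. A site could read HBS before it randomises.
- Section 7.5 names a group, not one person per couple. A reader might infer that the scorer has just watched that man's sperm bind on the PICSI dish. The text allows this but does not say it; only knowledge of the arm is documented.
- The four-monthly review by centre is not the only check. The re-scoring of thawed samples in the mechanistic laboratories is a second, off-site reading whose agreement with the clinic score is analysed. It is a partial safeguard: it covers some samples, follows freezing, and is not stated to compare arms.
- The subgroup analyses are labelled exploratory and hypothesis-generating (section 13.6.1).
- A reader might infer that the HBS interaction could appear or vanish through reading bias. The figures above do not support that: for assumed shifts up to 10 points the spurious interaction ratio stays between about 0.95 and 1.05.
- Section 9.6 cites logistical constraints, so reading HBS before allocation cannot be assumed possible everywhere.

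What remains is that the reader is unmasked, nothing requires the reading to precede allocation, and no stated check would show a difference between arms. The exploratory label covers the subgroup, but HBS also carries the primary mechanistic objective.

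**Conclusion.** The point stands as an avoidable weakness in how HBS is measured, not as a demonstrated bias. The protocol shows neither that arm-dependent reading occurs nor its size or direction. Under an assumed 5-point shift in one arm, the share at or below 65% moves from about 25% to about 19% or 32–33%, on either distributional model. The low-HBS odds ratio moves only to about 0.96 or 1.05 under no effect, which also rests on the borrowed prognostic ratio and the 24% live-birth rate. Band membership is therefore sensitive to reading, while the subgroup estimate is distorted modestly.

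A reader might also infer that the main result is at risk. It is not: HBS is neither a minimisation factor (section 9.6) nor an adjustment variable in the primary analysis (section 13.2.1), so the intention-to-treat live-birth comparison is unaffected. The change should be made, but the trial does not depend on it.

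**What to change.** In sections 7.5 and 10.4, state that, where workable, HBS is read and entered before the allocation is displayed. Where a site cannot do this, record on the Intervention CRF that HBS was read after allocation. This does not put HBS into the minimisation.

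In section 11.8.3, have the independent statistician, who is already unblinded, compare HBS by arm at each four-monthly check. The sample is prepared before allocation, so the two distributions should agree apart from chance.

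For the HBS subgroup and the mechanistic analyses, add a sensitivity analysis restricted to scores read before allocation.

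The cost is some SOP and CRF wording, a small change in the order of Day 0 work that some sites may be unable to make, and one extra comparison on data already harvested. Masked counting of stored slide images is an alternative but would need additional reader time.

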### 7.6 Primary Purpose

Increasing LBR ≥37 weeks' gestation following ICSI.

## 8. ELIGIBILITY

## 8.1 Centre eligibility

Participating centres will be IVF licensed hospitals.

The centre must be able to provide appointments in a dedicated clinic in which to see participants. There are 10 planned participating centres as described in Section 13.4.1. Recruitment rate will be monitored and optional additional centres may be added as required once the necessary approvals have been obtained.

## 8.2 Inclusion criteria for randomisation

- Couples able to provide informed consent
- Couples undergoing ICSI procedure
- Women :
  - BMI: 19.0 35.0 kg/m^2
  - FSH level 3.0 20.0 miU/ml and/or AMH ≥1.5 pmol/L
  - Age: 18 43
- Men:
  - Age: 18-55
  - Able to produce freshly ejaculated sperm for the treatment cycle

### 8.3 Exclusion criteria for randomisation

- Couples who have not consented prior to ICSI will be ineligible.
- Couples using non-ejaculated sperm.
- Couples using donor gametes.
- Men with vasectomy reversal; cancer treatment involving any chemotherapy and/or radiotherapy in the past two years.
- Previous participation in the HABSelect trial.
- Split IVF/ICSI procedures.
- If both FSH and AMH are tested and either of them falls outside the accepted range

#### 9. RECRUITMENT, ENROLMENT AND RANDOMISATION

#### 9.1 Recruitment process

Participants will be recruited from multiple research sites within the United Kingdom (see section 13.4.1). Research sites will be required to have obtained all necessary local management approvals, sign the model Agreement for Non-Commercial research (mNCA) and undertake a site initiation meeting prior to the start of recruitment into the trial. The recruitment target across all sites is 3730 participants over a period of 21 months.

#### 9.2 Eligibility and Informed Consent Process

#### 9.2.1 Identifying and approaching of potential participants

Process of identifying potential participants and inviting them to the study will be individualized for each participating centre and adapted to their routine practice. Potential trial participants will be identified in several ways:

- 1. Approached during standard IVF Fertility Centre visits, either during individual appointment with a clinician or a Patient Evening/Meeting.
- 2. From waiting lists, registries or review of case records. Participants identified by these means may be sent the personalised HABSelect Invitation letter inviting them to take part. This letter will include a brief introduction to the study and also a copy of the Couple Information Sheet and Informed Consent Form (CIS-ICF). Patients will be invited to contact their local research clinician to find out more information and to make an appointment to discuss the study further.
- 3. Self-referral after accessing information from the study website, which we will endeavour to link to other similarly-themed websites or from the posters displayed in each participating centre.

Couples will be identified as candidates for the HABSelect study by local IVF-ICSI licensed Fertility Centre staff if they have opted for or been advised to make use of ICSI based procedures. Normally, routine NHS assessment of ejaculate semen quality is sufficient for men to be selected for ICSI procedures over IVF. The clinical team will then check that the couple meets the inclusion and exclusion criteria (see section 8.2 & 8.3). Only couples meeting these criteria will be approached to provide consent to participate in the HABSelect study. Details will be recorded on the trial screening log.

#### 9.2.2 Informed Consent Procedures

The assessment of eligibility and the informed consent process will be undertaken by the principal investigator, or another suitably qualified member of the trial team who has received appropriate training and has been approved by the principal investigator as detailed on the delegation of responsibilities log. All staff involved in taking informed consent to the study will have a thorough knowledge and experience of Good Clinical Practice, issues around consent and will be fully conversant and trained in the study protocol. Informed, written consent for entry into the trial must be obtained prior to participant enrolment to the study.

The verbal explanation of the trial and CIS-ICF will be provided by the attending clinic staff for the patient to consider. This will include detailed information about the rationale, design and personal implications of the trial. They will be clearly advised that participation in the study is entirely voluntary with the option of withdrawing from the study at any stage, and that non-participation will not affect their usual care. Couples will be informed that they will be randomly allocated into standard (PVP-ICSI) or interventional (PICSI) groups, but both they and their clinical care staff will be unaware which group they are randomised to.

Following information provision, patients will have as long as they need to consider participation (a minimum of 24 hours is recommended) and will be given the opportunity to discuss the trial with their family and other healthcare professionals before they are asked whether they would be willing to take part in the trial. Assenting patients will be invited to provide informed, written consent. Where the patient has capacity to provide informed consent but is unable to sign or otherwise mark the consent form, we will follow the same procedure which the clinic adopts for such cases in regards to signing main HFEA consent forms for fertility treatment. If a translator is needed, the HABSelect research nurse will endeavour to make available the provision of a translation service\* in the spoken language of the participant per standard local NHS Trust arrangements to try to be as inclusive as possible to potential participants. The right of the patient to refuse consent without giving reasons will be respected. Further, the participant will remain free to withdraw from the study at any time without giving reasons and without prejudicing any further treatment.

\* It is difficult to predict the languages required as some of the NHS Trusts are located in areas with a high influx of asylum seekers from a multitude of ethnic background - all common languages will be endeavoured to be covered but we will not be translating our material as the NHS sites have reported that it is not uncommon that one member of the couple translates for the other. As there are no participant-completed questionnaires in this study we have taken advice and conclude that the provision of a translator is sufficient and indeed the best option to maximize inclusion. All other data collected on the participant is from routine collected data and is not affected by the language of the participant. A record of the consent process detailing the date of consent and all those present will be recorded in the participants' hospital notes. The original consent form will be filed in the

hospital notes (as per local practice), a copy retained in the Investigator Site File or study file containing patient identifiable data and a second copy of the consent will be given to the participants. With the couple's consent, the participant's GP will be notified using the REC approved GP letter provided. Once consent had been provided, the participants will be registered and recorded on the trial enrolment log.

Where valid, informed consent is obtained from the participants and if the participants subsequently becomes unable to re-affirm their consent by virtue of mental incapacity, the consent previously given is not enduring. Participants who lose capacity after informed consent has been obtained will be withdrawn from the trial without any further follow up or data collection.

No associated risks of the investigative procedure have been identified by the manufacturer of the interventional product. However if any further safety information which may result in significant changes in the risk/benefit analysis is identified, the CIS and Informed Consent Form (ICF) will be reviewed and approved accordingly. All participants who are actively enrolled on the study will be informed of the updated information and given a revised copy of the CIS/ICF to sign, confirming their wish to continue in the study. Copy of the consent forms will be given to the participant and the original added to the hospital notes.

